- 14) Unable to be prescribed stable dose of NSAIDs and/or tramadol based on medical history as ad lib use of OTC analgesics will be allowed in both groups after treatment
- 15) Current cigarette smoker
- 16) Unable to give informed consent
- 17) Non-English speaking

2.2 – Hypotheses

Hypothesis 1: We hypothesize that patients that are treated with BMAC and PRP will have improved KOOS subscale scores at 6 months and 12 months post treatment compared to patients treated with Gel-One® hyaluronate injections and relative to baseline. We hypothesize that both patients treated with BMAC and PRP and patients treated with Gel-One® will have improved KOOS subscale scores at 3 months post treatment relative to baseline.

A sample size of 30 total patients undergoing the treatment intervention has been established based on the power calculation ($\alpha = 0.05$, $\beta = 0.20$) of a previous study comparing allogeneic bone marrow MSCs to hyaluronic acid in 30 patients with knee osteoarthritis³⁰ and a preceding pilot study.³⁸ The primary outcome tool used in the study by Vega et al. has been demonstrated to have similar effect sizes at 6 and 12 months and similar smallest detectable differences compared to the KOOS scale in two different populations with knee-related deficits.^{39,40} A post-hoc power analysis will be completed, if necessary, to evaluate current findings and potentially plan for future studies with this specific study population.

Hypothesis 2a: We hypothesize that patients that are treated with BMAC and PRP will have improved NPRS scores at 3 months, 6 months, and 12 months post treatment compared to patients treated with Gel-One® hyaluronate injections and relative to baseline.

Hypothesis 2b: We hypothesize that patients that are treated with BMAC and PRP will have improved PROMIS Global Health scores at 3 months, 6 months, and 12 months post treatment compared to patients treated with Gel-One® hyaluronate injections and relative to baseline.

2.3 – Study Variables & Outcomes of Interest

Treatment Groups:

- N = 30 patients that will undergo treatment
- Group A: BMAC and PRP injections to target knee (n=15)
- Group B: Gel-One® hyaluronate injection to target knee (n=15)

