We recognize that there is risk for inherent bias within our study as patients are unable to be completely blinded to type of treatment he/she receives because each treatment procedure is distinctly different. Risk of selection bias is minimized by use of a randomized allocation schedule. Risk of influence on the patient when completing clinical outcome scales will be negated as the research team member administering the clinical outcome tools at 3, 6, and 12 months post-treatment will be blinded to group allocation.

ClinicalTrials.gov

As this study meets the FDAAA 801 definition of an “Applicable Clinical Trial” based on a drug and biologic, it is required that the study be registered on ClinicalTrials.gov. The Principal Investigator will register and activate the study account prior to enrollment, and all results will be entered upon study completion, followings statistical analysis, per the Results Database Guidelines.

2.5 – Statistical Analysis

Aim 1: Change in mean KOOS subscale scores over time based on treatment group

Total scores will be calculated for each patient using the KOOS subscales. The validated analysis guidelines for the KOOS instrument will be used. Patient’s total scores will be compared at baseline, 3 months, 6 months, and 12 months post treatment and compared by treatment group.

The statistical method that will be used is a Repeated Measures ANOVA (RM-ANOVA). This statistical strategy will allow us to control for the correlation in each individual’s measurements over time. The use of the standardized scales ensures that the outcome variable will be normally distributed, which will meet the underlying assumptions of the RM-ANOVA analysis. We will use the KOOS subscale score as the dependent variable, and the treatment assignment as the independent variable. If the distribution of gender is unequal across treatment groups after randomization, this statistical method will allow us to control for gender because changes in score will differ by gender. We will also be able to control for clinically meaningful variables such as patient age or BMI if there are differences in these variables between the two treatment groups at baseline.

Aim 2a: Change in mean NPRS score over time based on treatment group

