Total scores will be calculated for each patient using the NPRS. The NPRS instrument will be processed using the tool’s validated analysis guidelines. Patient’s total scores will be compared at baseline, 3 months, 6 months, and 12 months post treatment and compared by treatment group.

The statistical method that will be used is a RM-ANOVA. This statistical strategy will allow us to control for the correlation in each individual’s measurements over time. The use of the standardized scales ensures that the outcome variable will be normally distributed, which will meet the underlying assumptions of the RM-ANOVA analysis. We will use the NPRS as the dependent variable, and the treatment assignment as the independent variable. If the distribution of gender is unequal across treatment groups after randomization, this statistical method will allow us to control for gender

because changes in score will differ by gender. We will also be able to control for clinically meaningful variables such as patient age or BMI if there are differences in these variables between the two treatment groups at baseline.

Aim 2b: Change in mean PROMIS – Global Health score based on treatment group

Total scores will be calculated for each patient using the PROM Global Health scale (short form, version 1.1). The PROMIS global health instrument will be processed using the tool's validated analysis guidelines. Patient's total scores will be compared at baseline, 3 months, 6 months, and 12 months post treatment and compared by treatment group.

The statistical method that will be used is a RM-ANOVA. This statistical strategy will allow us to control for the correlation in each individual's measurements over time. The use of the standardized scales ensures that the outcome variable will be normally distributed, which will meet the underlying assumptions of the RM-ANOVA analysis. We will use the PROMIS global health scale as the dependent variable, and the treatment assignment as the independent variable. If the distribution of gender is unequal across treatment groups after randomization, this statistical method will allow us to control for gender because changes in score will differ by gender. We will also be able to control for clinically meaningful variables such as patient age or BMI if there are differences in these variables between the two treatment groups at baseline.

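### The planned repeated-measures ANOVA does not isolate the 6- and 12-month between-arm KOOS difference in Hypothesis 1; a baseline-adjusted model with a named contrast would

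*Combined protocol and SAP*

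**What the plan says.** Section 2.2, Hypothesis 1, says that "patients that are treated with BMAC and PRP will have improved KOOS subscale scores at 6 months and 12 months post treatment compared to" the Gel-One arm. At 3 months it claims only that both arms "will have improved KOOS subscale scores at 3 months post treatment relative to baseline".

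Section 2.5, Aim 1, is headed "Change in mean KOOS subscale scores over time based on treatment group". It states that total "scores will be compared at baseline, 3 months, 6 months, and 12 months post treatment and compared by treatment group", using a repeated-measures ANOVA, and then: "We will use the KOOS subscale score as the dependent variable, and the treatment assignment as the independent variable". No time term, interaction, contrast or deciding visit is named. Gender may be adjusted for if its distribution is unequal, and the model can "control for clinically meaningful variables such as patient age or BMI if there are differences in these variables". Baseline KOOS is one of the four repeated scores and is not named as a covariate.

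The same model wording serves the secondary outcomes: "We will use the NPRS as the dependent variable, and the treatment assignment as the independent variable" (Aim 2a) and "We will use the PROMIS global health scale as the dependent variable, and the treatment assignment as the independent variable" (Aim 2b). Hypotheses 2a and 2b place the between-arm difference at 3, 6 and 12 months.

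The documents differ on the visits for KOOS. Specific Aim 1 (section 1.2) and the primary outcome (section 2.3) list 3, 6 and 12 months; Hypothesis 1 confines the between-arm claim to 6 and 12.

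**The concern.** The primary hypothesis is about particular visits and has a direction. The planned model, as written, yields no test tied to either. If the analyst reports the group-by-time interaction, a significant result could come from any visit, including 3 months, where Hypothesis 1 claims no between-arm difference. If the analyst reports the treatment main effect, baseline and 3 months are averaged in and dilute a late effect. The choice among these, or visit-by-visit tests, could be made after the data are seen.

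Precision is also left unused. With 15 patients per arm, the baseline score is probably the most useful covariate available and is already collected from everyone. The plan instead admits covariates on observed imbalance, so the final model depends on the data.

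**Working it through.** **Inputs from the documents.** 15 treated per arm (section 2.1); alpha 0.05 (section 2.2); scores at baseline, 3, 6 and 12 months (section 2.5); 10 points as the minimal important KOOS change (sections 1.2 and 2.3).

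**Assumed.** The 10 points are used as a between-arm difference. SD 15, with 10 and 20 as a range; equal correlation r = 0.3 / 0.5 / 0.7 between any two visits; two-sided tests; complete data. Triplets below follow that order of r.

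**The plan's own figure.** N = 30 is borrowed from another study, and no KOOS effect or SD is given, so it can be neither reproduced nor refuted. Solved backwards, 15 per arm gives a two-sided t-test 80% power at 1.06 SD; for 10 points that means an SD of about 10/1.06 = 9.4.

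**1. Group-by-time reading.** F test on 3 and 3 × 28 = 84 df, with noncentrality λ = (n/2) Σ(δ_t − δ̄)² / [SD²(1 − r)], where δ_t is the arm difference at visit t.
- Difference 0/0/10/10 at baseline/3/6/12 months: Σ = 4 × 25 = 100; λ = 7.5 × 100 / [225(1 − r)] = 4.76 / 6.67 / 11.11; power 40 / 55 / 79%. The middle value is 54.5% by formula and 54.9% by simulation.
- Difference at 3 months only, 0/10/0/0: Σ = 56.25 + 3 × 6.25 = 75; λ = 3.57 / 5.00 / 8.33; rejects 31 / 42 / 65%.

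**2. Treatment main-effect reading.** For 0/0/10/10 the averaged difference is (0 + 0 + 10 + 10)/4 = 5 points. SE = 15√[(2/15)(1 + 3r)/4] = 3.77 / 4.33 / 4.82 on 28 df; power 25 / 20 / 17%.

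**3. Named contrast on the 6/12-month mean.** SE = 15√[(2/15)V], with a further factor 1 + 1/26 inside the root for the adjusted version (average chance baseline imbalance).

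| Contrast | V | SE (points) | 95% half-width | Power, 0/0/10/10 |
|---|---|---|---|---|
| Change from baseline (28 df, t = 2.048) | 1 + (1+r)/2 − 2r = 1.05 / 0.75 / 0.45 | 5.61 / 4.74 / 3.67 | 11.5 / 9.7 / 7.5 | 41 / 53 / 75% |
| Post-treatment mean, unadjusted (28 df) | (1+r)/2 = 0.65 / 0.75 / 0.85 | 4.42 / 4.74 / 5.05 | – | 59 / 53 / 48% |
| Baseline-adjusted (27 df, t = 2.052) | (1+r)/2 − r² = 0.56 / 0.50 / 0.36 | 4.18 / 3.95 / 3.35 | 8.6 / 8.1 / 6.9 | 64 / 69 / 82% |

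For a difference at 3 months only, the adjusted contrast rejects 5% of the time, as it should. With complete data and a baseline-by-visit term, the mixed-model contrast equals this ANCOVA.

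**4. Where the power gain comes from.** At r = 0.3 the unadjusted post-treatment contrast already reaches 59% against 40% for the interaction, and the covariate adds about 5 points. At r = 0.7 neither unadjusted contrast (48% and 75%) beats the interaction (79%); the adjusted one does, narrowly (82%). The split therefore depends on r.

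**5. Where the contrast gains nothing or loses.**
- Difference at 12 months only: interaction 31 / 42 / 65%, adjusted contrast 21 / 23 / 30%.
- Growing effect 0/0/5/10: interaction 28.5 / 39 / 61%, adjusted contrast 41 / 45 / 58%. At r = 0.8 it is 80% against 72%.
- Flat 0/0/10/10 at r = 0.8: 93% against 92%.

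**6. Sensitivity, 0/0/10/10.** At r = 0.5, adjusted contrast against interaction: 96% against 90% at SD 10, and 45% against 32% at SD 20. With correlation decaying by visit (0.5 or 0.7 between adjacent visits, SD 15), the adjusted SE is 4.72 or 4.59, against 6.42 or 5.52 for change from baseline.

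**7. Aims 2a and 2b.** For an equal difference of 10/15 = 0.67 SD at all three follow-up visits, the interaction has 31 / 42 / 65%. The adjusted contrast on the three-visit mean, V = (1+2r)/3 − r², has 74 / 76 / 87%.

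Simulation of 20,000 trials per setting agreed with the formulas to within about one percentage point for the interaction and the 6/12-month contrasts, in the settings simulated.

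**The case against.** A reader might infer that the planned ANOVA does not test Hypothesis 1 at all, or is invalid. The documents do not support that. Baseline enters as a repeated level, so the interaction works on within-patient change and is valid under randomisation, and it has real power for the hypothesised pattern. The fault is that it does not isolate the 6- and 12-month difference.

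Group-by-time is also never named. The Aim 1 heading favours that reading, but the Aim 2b heading lacks the phrase about time, and the sentence about comparing scores at each visit could mean visit-wise tests. Those would address 6 and 12 months. This stands as a possible reading, but no such tests are defined.

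Rejecting for a 3-month-only difference is off target for Hypothesis 1 but not for Specific Aim 1, which includes 3 months. That also stands, and the two must be reconciled before a contrast is named.

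A reader might further infer that baseline adjustment always gives more power, or is the sole source of the gain. Steps 4 and 5 show otherwise. A contrast of the 6/12-month mean against the baseline/3-month mean (variance factor 1 − r, 84 df) would have 58 / 72 / 91% with no covariate, above the adjusted contrast at r = 0.5 and 0.7. It answers a different question if the arms already differ at 3 months.

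Finally, the mean of 6 and 12 months does not itself show which visit differs. That is fair, and is why separate visit estimates are needed beside it.

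The list of covariates is illustrative and does not rule out baseline KOOS. But the stated trigger is imbalance, so adjustment for it is not planned.

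**Conclusion.** The point holds as under-specification with a better method available at almost no cost. As written, section 2.5 does not isolate the between-arm difference at 6 and 12 months: the interaction shows neither visit nor direction, the main effect halves a difference confined to those visits, and visit-wise tests are not specified. A significant interaction would not establish the hypothesised benefit.

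The firm gain from the change is a directly interpretable estimate with a smaller standard error than change from baseline, at every correlation below about 0.94 under equal correlation. Higher power than the interaction is usual but conditional: it is absent at r of about 0.8, and reversed for a 12-month-only effect or, at r of 0.7 or more, for an effect growing from 6 to 12 months. All power and interval figures rest on the assumed SD and correlation, the use of 10 points as a between-arm difference, and complete data. This should be fixed, but it does not invalidate the trial.

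**What to change.** Before outcome data are analysed, replace the model paragraph in section 2.5:

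- For each KOOS subscale, analyse change at 3, 6 and 12 months in a repeated-measures mixed model with baseline score, baseline-by-visit, treatment, visit and treatment-by-visit, an unstructured covariance and small-sample degrees of freedom.
- Fix any further covariates (gender, age, BMI) in advance, not by observed imbalance.
- Reconcile the visits in Hypothesis 1 with those in Specific Aim 1 and the primary outcome. If Hypothesis 1 governs, name the between-arm contrast on the mean of 6 and 12 months as its test.
- Report separate 6- and 12-month between-arm estimates with confidence intervals, and within-arm changes including 3 months. State whether the claim requires benefit at both visits. A 12-month-only contrast is not a substitute, because it leaves 6 months untested.
- Use the same model for NPRS and PROMIS with the contrast on the mean of 3, 6 and 12 months, to match Hypotheses 2a and 2b.

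The cost is SAP wording and a few degrees of freedom. No visits, patients or instruments are added, and SAS 9.4 is already planned. Multiplicity across the five KOOS subscales is a separate matter that this change does not settle.

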The following data points will be collected for patients who choose to participate in the study at McConnell Spine, Sport, and Joint Center (see Table 1). Patient data will be collected via the electronic medical record at the study physician's practice, as well as by means of study specific data collection forms (see Appendices). Only the study staff will have access to the paper data collection forms and the Research Electronic Data Capture (REDCap) database created solely for use in this study. Exported REDCap patient data will be de-identified upon study completion, prior to statistical analysis using SAS 9.4 (SAS Institute Inc., Cary, NC, USA).

Demographics:

- Age, gender, and body mass index (BMI)

Relevant clinical information or past medical history:

- Relevant past medical history related to the involved knee including previous surgical procedures, previous intraarticular injections, other treatments, and course of knee pain
- Kellgren-Lawrence grade of KOA via standing radiograph of the target knee
- Platelet count via complete blood count (Group A only)

Other relevant therapies received following the study treatment:

- Therapies received for the target knee including use of over the counter medications (i.e., Advil, Motrin, or Tylenol), prescription anti-inflammatories or NSAIDs (i.e., Mobic, Naprosyn, Celebrex, or Voltaren), narcotics (i.e., Tramadol, Percocet, Vicodin, or others), or physical therapy

Primary outcome measures:

- Change in KOOS subscale scores which will objectively measure pain, function, and quality of life indicators at 3 months, 6 months and 12 months post treatment (see appendix 4.1 for KOOS scale)

Mean values for the KOOS subscales have been studied in a population-based sample (i.e., not specific to whether those surveyed actually had knee complaints).⁴¹ The population-based sample of subscale scores (i.e., range of 0-100 with a score of 100 representing the best possible score) in the approximate age group of this study ranged from 61 to 89.5, which also varies by gender.⁴¹ A change in 10 points has been suggested³⁶ and utilized³⁷ to demonstrate a minimal clinically important difference (i.e., decline or improvement) in each KOOS subscale.

Secondary outcomes measures:

- Change in pain scores as measured by the NPRS at 3 months, 6 months, and 12 months post treatment (see appendix 4.2 for NPRS scale)

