3. All patients will complete a follow up visit at approximately 6 months (+/- 14 days) following the date of the treatment provided for completion of the primary and secondary outcome tools.
4. All patients will complete a follow up visit at approximately 12 months (+/- 14 days) following the date of the treatment provided for completion of the primary and secondary outcome tools.

Data Collection

Time point	Measurement	
Baseline ≤14d from presentation or at presentation	1. Demographic information including gender, age, and BMI 2. Relevant past medical history related to the involved knee including previous surgical procedures, previous intraarticular injections, other treatments, and course of knee pain (i.e., primary osteoarthritis or from previous traumatic injury) 3. Kellgren-Lawrence grade 4. Platelet count -Group A only 5. KOOS subscales 6. NPRS 7. PROMIS Global Health (short form, version 1.1) scale	
RANDOMIZATION – 15 patients per group		
Treatment Delivered ≤30d from Baseline	Group A (n=15) Single episode of BMAC and PRP injections to the target knee	Group B (n=15) Single injection of Gel-One® hyaluronate to the target knee
3 months (+/- 7 days) after treatment	1. KOOS subscales 2. NPRS 3. PROMIS Global Health scale 4. Other relevant therapies received following the study treatment	
6 months (+/- 14 days) after treatment	1. KOOS subscales 2. NPRS 3. PROMIS Global Health scale	

	4. Other relevant therapies received following the study treatment
12 months (+/- 14 days) after treatment	1. KOOS subscales 2. NPRS 3. PROMIS Global Health scale 4. Other relevant therapies received following the study treatment

Risks:

Risks are typical for bone marrow aspiration, blood draw, and intraarticular knee injection and include the following:

Common or likely for blood draw in Group A (participants who will receive BMAC and PRP injections to the target knee):

- Momentary discomfort at the site of the blood draw
- Bruising, redness, swelling, or bleeding at the site of the blood draw
- Feeling of lightheadedness when the blood is drawn

Rare for blood draw in Group A (participants who will receive BMAC and PRP injections to the target knee):

- Infection at the site of the blood draw

Rare for bone marrow aspiration in Group A (participants who will receive BMAC and PRP injections to the target knee):

- Excessive bleeding, particularly in people with low numbers of a certain type of blood cell (platelets)

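### Section 2.5 lets observed baseline imbalance decide whether gender, age or BMI enter the RM-ANOVA; name one primary model, with its visit terms and baseline adjustment, before outcomes are seen

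*Combined protocol and SAP*

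**What the plan says.** Section 2.5, Aim 1 ("Change in mean KOOS subscale scores over time based on treatment group") names a repeated-measures ANOVA over baseline, 3, 6 and 12 months. The model is described in one sentence: "We will use the KOOS subscale score as the dependent variable, and the treatment assignment as the independent variable".

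Two conditional sentences follow. The first is "If the distribution of gender is unequal across treatment groups after randomization, this statistical method will allow us to control for gender", and the reason given is "because changes in score will differ by gender". The second says the team can also adjust for clinically meaningful variables "such as patient age or BMI if there are differences in these variables between the two treatment groups at baseline". Aims 2a and 2b repeat both sentences for NPRS and PROMIS.

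Related text elsewhere:
- Section 2.3 says population KOOS subscale means "in the approximate age group of this study ranged from 61 to 89.5, which also varies by gender".
- The Data Collection table in section 2.4 lists "Demographic information including gender, age, and BMI" at baseline.
- Randomization (section 2.4) is 1:1 and blocked, with no stratification stated. The person who will run the analyses also writes the allocation schedule.
- Hypothesis 1 (section 2.2) predicts "improved KOOS subscale scores at 6 months and 12 months post treatment compared to patients treated with" Gel-One. Specific Aim 1 and the primary outcome definition also include 3 months, and every hypothesis has a part relative to baseline.

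**The concern.** The text does not define one analysis. Neither inequality of gender nor difference in the other variables has a threshold. The list is open, no version is called primary, and nothing says whether a covariate enters as a main effect or crossed with visit. Nothing fixes the choice before outcomes are seen, and blinding does not protect it, because the analyst writes the allocation schedule.

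Observed imbalance is also a poor trigger. The case for adjusting is that a covariate predicts outcome, which can be judged in advance. The plan already asserts this for gender and already collects it. At stake are a reproducible primary result, control of the 5% error rate if the choice is made late, and some efficiency.

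**Working it through.** **Inputs.** From the plan: 15 treated per arm, visits at baseline, 3, 6 and 12 months, alpha 0.05, and a 10-point minimal important KOOS change. The covariate rule carries no figure of its own to reproduce. Assumed, because the plan gives none: proportion of women, covariate R², SD, baseline correlation, two-sided tests, and the 10 points taken as the between-group difference.

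**1. How often the trigger applies.** With p the proportion of women, P(equal counts) = Σ Bin(k; 15, p)². At p = 0.5 this is C(30,15)/2³⁰ = 0.144; at 0.60 and 0.65 it is 0.148 and 0.152. The arms therefore differ in gender count in about 85% of trials. They differ by three or more women in 34-36%, and reach Fisher p < 0.05 in about 1.6%. For age or BMI singly, P(|d| > 0.5) = 2·P(t₂₈ > 0.5·√7.5) = 0.18. So the trigger can mean nearly always or nearly never.

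**2. Main effect or crossed with visit.** A baseline covariate has one value per patient. Entered as γx, it cancels from any within-patient difference: (y₂ + γx) − (y₁ + γx) = y₂ − y₁. In one simulated complete data set the group-by-time F was:

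| Model | F | df |
|---|---|---|
| No covariate | 0.836 | 3, 84 |
| Gender main effect | 0.836 | 3, 84 |
| Gender crossed with visit | 0.931 | 3, 81 |

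In a second data set the 12-month group contrast was 2.378, 2.378 and −1.552 in the same order. The plan's reason, that changes differ by gender, needs the crossed term.

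**3. Type I error, contrast at one visit** (40,000 null trials per column; gender, age and BMI independent; joint R² assumed):

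| Procedure | R² 0 | 0.15 | 0.30 | 0.50 |
|---|---|---|---|---|
| Preset rule, adjust if \|d\| > 0.5 | 5.1% | 4.3% | 3.5% | 2.7% |
| Fixed gender | 5.3% | 5.0% | 4.9% | 5.0% |
| Better of unadjusted and gender-adjusted | 5.9% | 6.1% | 6.4% | 6.9% |
| Better of unadjusted and fully adjusted | 6.6% | 7.1% | 7.6% | 8.5% |

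For the group-by-time F with crossed covariates (20,000 trials; joint share of change variance 0 to 0.5), the preset rule gives 5.1% falling to 3.1%, the fixed full model 5.0-5.1%, and the better of none and full 6.7-9.3%. The unadjusted F, run without a sphericity correction, is itself 5.9% at the top of that range, so not all of the 9.3% comes from choosing.

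**4. Power at one visit.** The error variance is 2(1 − ρ)σ² for a change score and (1 − ρ²)σ² with baseline as covariate, a ratio of (1 + ρ)/2 = 0.75, 0.80, 0.85 for ρ = 0.5, 0.6, 0.7. Simulated power (20,000 trials) for 10 points, SD 15, each covariate explaining 5% of change variance:

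| Analysis | ρ 0.5 | 0.6 | 0.7 |
|---|---|---|---|
| Change score, imbalance rule | 40.8% | 48.4% | 61.0% |
| Change score, fixed gender | 42.7% | 50.9% | 62.9% |
| Baseline score only | 51.4% | 57.8% | 67.3% |
| Baseline score and gender | 52.4% | 58.6% | 68.6% |

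Last row minus first: 11.6, 10.2 and 7.6 points. Replacing the trigger alone (row 2 minus row 1): 1.9, 2.5 and 1.9. Adding gender to baseline (row 4 minus row 3): 1.0, 0.8 and 1.3. With SD 20 the first comparison is 25.4/30.4/38.7% against 33.7/37.8/44.8%, a gain of 8.3, 7.4 and 6.1 points.

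If no covariate predicts anything (SD 15), baseline only gives 51.7/57.5/68.4% and baseline plus gender 50.0/55.9/66.5%, a loss of 1.7, 1.6 and 1.9 points.

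**5. Why the crossing must be written down.** With complete data and unstructured covariance, the fully crossed model gives the same treatment contrasts as visit-by-visit ANCOVA (9.500, 8.893, −0.117 both ways in a simulated data set). With baseline and gender as main effects only, they become 8.632, 7.989 and 1.813.

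**The case against.** **The rule looks only at baseline, so it does no harm.** This stands for a preset cut-off. A reader might infer that adjusting on imbalance inflates type I error in itself; step 3 shows the opposite. What remains is that the plan presets no cut-off, and its wording says what the method can do rather than what will be done.

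**The inflation can be overstated.** Also true. Taking the best of all eight subsets of the three variables gives 7.7-13.8%, but that analyst ignores balance, which the text does not license. It is a hypothetical ceiling and carries no weight here. An analyst who picks a cut-off after seeing outcomes but applies it consistently to all three variables reaches 6.9-9.2% (6,000 trials per row). One choosing only between unadjusted and the |d| > 0.5 rule reaches 5.2-5.9%. Nothing in the documents suggests that anyone intends to choose this way; they only leave it possible.

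**Gender is not clearly worth including.** Largely right on size: it adds about 1 point of power or costs 1-2. The section 2.3 remark concerns score levels in a population sample, and level differences cancel in change scores. Only the statement in section 2.5 that changes differ by gender supports a gender-by-visit term. Prespecifying no demographic term would close the same gap.

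**Baseline adjustment is a separate matter.** In part. But baseline is a repeated level in the planned RM-ANOVA, so a covariate set cannot be fixed without saying how baseline is handled, and that is where most of the gain lies. Moving baseline out of the outcome must not drop the 3-month KOOS comparison or the relative-to-baseline estimates that the aims and hypotheses call for.

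**Conclusion.** The concern holds as a gap in prespecification, and the plan should be changed. Section 2.5 lets observed imbalance settle the covariates, with no threshold, closed list, primary version, visit terms or timing.

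Its size is moderate and conditional. With a preset cut-off, error is about 5% falling to 3%. If the choice between unadjusted and adjusted models follows sight of outcomes, error is about 6-9% per test for covariate R² between 0 and 0.5. As a main effect, gender adjustment would leave the group-by-time test untouched and fail the plan's own reason for it.

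The proposed model gains about 8-12 points of power at SD 15 and about 6-8 at SD 20. A reader might credit gender adjustment with that gain; it comes almost wholly from the baseline score. R², SD and correlations are assumptions, and the error and power figures are for complete data.

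**What to change.** In each aim, delete both conditional sentences and, before outcome data are exported for analysis, state one primary model to be used whatever the observed balance:

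- **Outcome:** scores at 3, 6 and 12 months.
- **Terms:** treatment, visit, treatment-by-visit; baseline value of the same score and baseline-by-visit; gender and gender-by-visit, on the plan's own statement that changes differ by gender. If the sponsor does not hold that view, prespecify no demographic term.
- **Covariance:** unstructured across the three visits, with a small-sample degrees-of-freedom method such as Kenward-Roger.
- **Reported:** treatment contrasts at 3, 6 and 12 months for every score, with 6 and 12 months identified as the KOOS superiority contrasts of Hypothesis 1; and within-group change from baseline at each visit, for the relative-to-baseline parts of the hypotheses.
- **Sensitivity only:** the same model adding age and BMI, each crossed with visit.

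The cost is SAP wording and two residual degrees of freedom per visit (28 to 26), with no new data. If gender predicts nothing, including it loses about 1-2 points of power against baseline score alone.
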